#### **B4. Partner Inclusion Criteria:**

One goal of the proposed research is to determine whether collateral report of parent-child functioning is feasible, as this is a best practice in family functioning research. At the baseline assessment, Veterans will be asked to complete a consent for partner contact and release of information form to allow study staff to contact the partner. If the Veteran agrees, partners will be called and offered the chance to complete a brief assessment at pre-and post-treatment. Partners are eligible to participate in the phone interview if they are over 18 (assessed verbally) and give verbal assent to participate (or agree to participate using the online assessment system).

#### **B5. Aim 1 (Months 0-18). Number of Subjects: 32.**

[figure not shown]
**Obtain and incorporate expert clinician and Veteran feedback on credibility, acceptability, and satisfaction with the intervention to ensure Veteran-friendly SAHP manual, materials, and processes.** Aim 1 will be accomplished through two rounds of expert panel review of the treatment/MIA manual and two rounds of pilot testing of the treatment/MIA for Veteran feedback (see Figure 1). First, the SAHP manual will be reviewed by a panel of expert clinicians who will provide feedback. Second, the revised SAHP manual will be piloted for Veteran feedback in 1 group of

women Veterans ( $n = 8$ ) and 1 group of men Veterans ( $n=8$ ). Third, the expert panel will convene again for consensus decision making regarding the Veteran feedback and additional adaptation of the SAHP manual. They will also review and provide feedback on the MIA manual and forms at this time. Finally, the revised manuals will be piloted a second time in 1 group of women Veterans ( $n = 8$ ) and 1 group of men Veterans ( $n = 8$ ) to ensure that revisions improved Veteran satisfaction with the treatment. Total N for Aim 1 is 32 Veterans.

## **B6. Aim 1 Procedure for intervention refinement:**

**Expert Panel 1:** The first panel review will be a pre-assessment and refinement of materials. SAHP materials will be disseminated in month 1. Consultants will review and provide written feedback on the SAHP manual and they will be convened for a tele-conference in month 3 for a consensus discussion of needed modifications based on their considerable expertise and with consideration for effective presentation of material and ease of use by VHA clinicians. The manual will be revised accordingly.

Figure 2. Study design

**Pilot Group 1:** Veteran feedback (see measures and data sources) will be obtained through a pilot trial of SAHP in which they will assess the acceptability and credibility of SAHP strategies/content after each session. Investigators and facilitators will review session procedures and will use a template to make detailed notes after each module on phrasing, clarity, and participant engagement with material. There will be two pilot groups: 1 in women and 1 in men.

**Expert Panel 2:** The Veteran feedback from the first pilot round will be incorporated into a revised treatment manual during a second panel review. The panel will be provided with a summary of Veteran feedback and proposed manual revisions. Expert consultants will review and provide written feedback on the proposed revisions to the SAHP manual, and they will convene again by teleconference (month 12) for a consensus discussion of needed modifications. During the second panel the expert consultants will also evaluate and provide feedback on the MIA manual and forms. Veteran feedback on the MIA will not be assessed until the Open trial (Aim 2) because staff will still be training and achieving competence in MIA throughout Aim 1 (see Aim 1 MIA training). PI [name] and Co-I's [name], [name] and [name] will make final revisions to the SAHP and MIA manual according to this feedback.

**Pilot Group 2:** The revised SAHP treatment will be piloted for Veteran feedback a second time to ensure revisions improve credibility, acceptability and satisfaction. As in pilot group 2 there will be two pilot groups held at this stage: 1 in women and 1 in men. Veteran feedback

will be used to make any final modifications to the treatment manual prior to the open trial.

**B7. Aim 1 Procedure for pilot groups:** The project coordinator and Research Technician will administer all assessment materials to Veteran participants. The PI and post-doctoral fellows will facilitate treatment groups.

Recruitment: Recruitment will use 2 main strategies: 1) Direct recruitment at local events, provider referrals, and flyers posted. 2) The study analyst will utilize VA administrative databases to request a list of all OEF/OIF/OND Veterans in our catchment area who have screened positive for PTSD on the Primary Care-PTSD Screen or who have a diagnosis of PTSD in their problem list. These Veterans will receive a letter informing them of the study and providing an opportunity to opt out of future contact.

Following standard VA procedures and data pull approval processes, the study analyst will pull the contact information of all Veterans in the Central TX VA catchment area with PTSD in their problem list, with dependents where possible, and without the exclusion criteria in their problem list. This will result in a large data pull, from which we will randomly select two batches to receive letters notifying them of the study and that they may receive a call. As one of the study aims is to measure the feasibility of recruiting veterans in the target group, we do not know how many veterans will truly meet inclusion criteria and how many will be interested. Starting with the larger group allows us the ability to estimate our needs better in the future, while also enhancing likelihood of recruiting success.

Eligibility screening: Those Veterans who are interested in participating will complete inclusion eligibility screening by telephone (15-20 minutes). Those who are eligible and interested based on the phone screen will be scheduled for an intake assessment (MIA).

Participant Remuneration: \$50 pre- and post-assessment, \$10 per post-intervention assessment for a total of \$180. The \$10 per post-intervention assessment is not reimbursement for participating in the intervention, but for time spent completing measures after each session. Partners will receive \$20 for time spent completing each of 2 phone/web-based assessments.

Measures and Data sources for Pilot Groups (see Appendix for copies of measures): Credibility, acceptability, and satisfaction will be assessed with 4 measures. 1) The Credibility/Expectancy Questionnaire (CEQ) will measure intervention credibility after each session. This measure has high internal consistency and test-re-test reliability. Four questions on an 8-point Likert scale inquire about the logical nature of the intervention, willingness to recommend it to others, and expectations for the success of the intervention. Items are summed and scored, with higher scores representing greater credibility (possible range 0-32). 2) The Client Satisfaction Questionnaire-8 (CSQ) assesses acceptability post-treatment. Eight items are scored on a 4-point scale

inquiring about quality of services, treatment satisfaction, and willingness to recommend the treatment to others. Ratings are summed, with higher scores representing greater acceptability ratings (possible range 4-32). This measure is commonly used in both clinical trials and program evaluation, and has been shown to correlate with treatment attendance and outcomes. It takes approximately three minutes to complete.

Evaluations of the measure found it to be reliable, with high coefficient alphas (.83-.93) to support internal consistency, and that it evidences positive construct validity with other measures of satisfaction. Where available, mean CSQ ratings can also be compared against norms from other studies in similar populations. 3) SAHP specific satisfaction questionnaire: Veteran feedback will be elicited after sessions using an open-ended measure to assess satisfaction with SAHP strategies and content.

Satisfaction will be evaluated via Veteran ratings of how helpful the session was, how helpful the homework was (0 = “not at all helpful,” 8 = “definitely helpful”), whether they learned anything during the session, and which components of each session were helpful or unhelpful. A modified version of this form will evaluate satisfaction with the MIA during the open trial. 4) Clinician notes after sessions will document phrasing and clarity of materials, and participant engagement with material. Clinicians will complete a template after each session documenting how role plays, examples, and language was received, any suggesting any changes.

Aim 1 Analysis Plan: Credibility ratings (CEQ) will be averaged to determine overall ratings for each session. Acceptability ratings (CSQ) will be averaged to determine overall acceptability and satisfaction for the intervention. The item-level and overall means on the CEQ/CSQ will be examined in concert with feedback from the open-ended SAHP specific questionnaires to guide further refinements to the treatment manual. Specifically, matrix displays will be used to organize and examine the qualitative and quantitative feedback from Veterans. Matrix displays allow for within-case analyses (i.e., comparing a participant’s satisfaction with different sessions) as well between-case analyses (i.e., comparing satisfaction for a session across groups) and comparisons with the quantitative data (CEQ, CSQ). A matrix format for entering and displaying data, which may include words, phrases, or direct quotes, will be based on the open-ended questions, with each of the primary topics (e.g., satisfaction with material, comments on practice assignments, intervention acceptability, etc.) having a separate matrix to identify common themes and concepts of importance. The analysis will guide adaptations to the intervention manuals. Data will be summarized for presentation to the expert panel that will evaluate additional refinements to the treatment manual. If major changes are made to the intervention in response to feedback from pilot 1, we will also examine whether there are changes in credibility and acceptability ratings from pilot 1 to pilot 2.

Motivational Interviewing Assessment (pre-treatment): The study assessor will be the post-doctoral associate and may include other CoE trainees (fellows and interns). The pre-treatment assessment will be conducted as a MIA which sandwiches two 20 min MI sessions around a structured clinical intake.

Aim 1 MIA training: Throughout aim 1, study assessors will be developing their MI skills and the focus will be on attaining MI competency. During this phase a project specific MIA protocol and manual will be developed and tested for use in the pilot and open trial and the future RCT. [name] (CO-I) will provide centralized training in MI and the MIA to study staff beginning with a two-day training, followed by intensive fidelity coding and coaching. [name] will collaborate with the study team members to draft the assessment protocol and manual and will provide ongoing consultation and training to staff in MI and the MIA for both assurance of training goals and fidelity to the model during the pilot and open trial.

Table 2: Research Timeline

| Quarters   | Yr 1 |   |   |   |   | Yr 2 |   |   |   | Yr 3 |    |    |    |
|--|------|---|---|---|---|------|---|---|---|------|----|----|----|
|  | 0    | 1 | 2 | 3 | 4 | 5    | 6 | 7 | 8 | 9    | 10 | 11 | 12 |
| Pre-Award Activities (completed)                          |      |   |   |   |   |      |   |   |   |      |    |    |    |
| • IRB Application and staff hiring                               |      |   | X | X |   |      |   |   |   |      |    |    |    |
| Motivational Interviewing Assessment Training (completed) |      |   |   |   |   |      |   |   |   |      |    |    |    |
| • 2 day MIA training   |      |   | X |   |   |      |   |   |   |      |    |    |    |
| • Staff test out for MIA competency                              |      |   |   | X |   |      |   |   |   |      |    |    |    |
| • SAHP/MIA protocol complete                                     |      |   |   |   | X |      |   |   |   |      |    |    |    |
| • All staff rated competent on MIA                               |      |   |   |   |   | X    |   |   |   |      |    |    |    |
| • Expert panel review of MIA protocol                            |      |   |   |   |   |      | X | X |   |      |    |    |    |
| • MIA manual and forms finalized                                 |      |   |   |   |   |      |   |   | X |      |    |    |    |
| Aim 1) Refine and Pilot test SAHP (completed)             |      |   |   |   |   |      |   |   |   |      |    |    |    |
| • Panel review of treatment manual                               |      |   | X |   |   |      |   |   |   |      |    |    |    |
| • Refine Manual  |      | X | X |   |   |      |   |   |   |      |    |    |    |
| • Recruitment  |      |   | X | X |   |      |   |   |   |      |    |    |    |
| • Pilot groups (n = 8 men and 8 women)                           |      |   |   | X | X |      |   |   |   |      |    |    |    |
| • 2 nd Panel review/Refine manual                     |      |   |   |   | X | X    |   |   |   |      |    |    |    |
| • Pilot groups (n = 8 men and 8 women)                           |      |   |   |   | X | X    | X |   |   |      |    |    |    |
| • Finalize treatment manual                                      |      |   |   |   |   | X    | X |   |   |      |    |    |    |
| Aim 2) Open Trial and Feasibility evaluation (ongoing)    |      |   |   |   |   |      |   |   |   |      |    |    |    |
| • Recruitment  |      |   |   |   |   | X    | X |   |   |      |    |    |    |
| • Pilot groups (n = 24-30 men; 24-30 women)                      |      |   |   |   |   |      | X | X | X | X    | X  |    |    |
| • Analysis of findings   |      |   |   |   |   |      |   |   | X | X    |    |    |    |
| • Dissemination of Results                                       |      |   |   |   |   |      |   |   |   | X    | X  |    |    |
| • Application for IIR for clinical trial                         |      |   |   |   |   |      |   |   |   | X    | X  |    |    |

### **B8. Aim 2 (Months 18-36) (N = 48-60 Veterans; N=48-60 partner phone assessments)**

**Evaluate feasibility of study recruitment, retention, assessment procedures and proposed methods of the SAHP intervention.** Aim 2 will be accomplished through an open trial of the final SAHP intervention in 3-5 groups of female Veterans (n = 24-30) and 3-5 groups of male Veterans (n = 24-30; total N = 48-60). Research questions to be answered include: 1) feasibility of group modality, viability of gender specific cohorts/recruitment of women, timing and location of group sessions, and barriers to participation, 2) Veteran perceptions of/satisfaction with MIA, proposed RCT outcomes measures, and collateral partner report of parent-child functioning, 3) Feasibility of MIA as evidenced by clinician experiences using the MIA and clinician fidelity ratings throughout the open trial. MIA fidelity coding will be conducted by [name]. Feasibility of collateral partner report of parent-child functioning. 4) Preliminary test of whether SAHP results in improvements to parenting behaviors, parenting satisfaction and family functioning.

**B9. Procedures:** All group procedures including recruitment, eligibility screening, inclusion and exclusion criteria for Aim 2 are the same as described above in Aim 1, with one exception – groups may now be facilitated by one facilitator (PI or post-doctoral fellow).

**Measures and Data sources:** Feasibility and acceptability will be assessed with three measures: 1) Number and rates of Veterans contacted, screened, assessed, enrolled, retained; 2) Veteran reasons for opting out or dropping out. 3) Veteran ratings of their satisfaction with treatment (CSQ; SAHP satisfaction). Feasibility and satisfaction with the pre-treatment MIA will be evaluated using the Client Evaluation of Motivational Interviewing Scale (CEMI) and a study specific post-assessment feedback form that will assess for satisfaction (see appendix). The CEMI is an 11-item self-report measure of client perceptions of clinicians' use of MI during their session. Internal consistency is high across the two factors ( $\alpha = .88$ , relational;  $\alpha = .91$ , technical). Evaluations of CEMI validity found that client's experiences of clinician MI fidelity was generally consistent with other measures. MIA fidelity ratings based on the MIA Interview Rating Guide will be provided by [name] to determine feasibility of clinicians providing MIA. Feasibility of collateral partner report of parent-child functioning will be determined based on the number of Veterans with a partner who could complete collateral report, the number who consent to partner contact, and data completion rates for this aspect of the study.

Five measures will be used as a preliminary assessment of treatment outcomes and a sixth measure will be used to understand co-morbidity in the study sample. These measures will be completed at intake and after session 8. In the case of drop-out, the post-treatment assessment will be scheduled within one week of what would have been session 8 and this will be done in person or over the phone. 1) The Parenting Stress Index, 4th edition (PSI) is a 120-item measure on a five-point Likert scale yielding a parent and child domain scale measuring stress related to parent and child characteristics including relevant subscales. The PSI includes a scale examining support from a parenting partner. The PSI has high reliability coefficients ( $\alpha = .75-.88$ ), high internal consistency ( $\alpha = .96$ ), and high test-retest reliability. The measure has been validated across a variety of population, and takes 10 min. to complete. 2) The Alabama Parenting Questionnaire (APQ), contains 42 items examining positive and negative discipline and other parenting practices and takes 10 min. to complete. The measure evidences satisfactory reliability ( $\alpha = .80-.92$ ), and discriminant and convergent validity. The parent report converges well with concurrent observational ratings of parenting. 3) The 12-item general family functioning scale of the Family Assessment Device (FAD) measures general family functioning and consists of statements about family functioning that respondents answer via a 4-point Likert scale and takes 5 min. to complete. Responses are added together, then divided by twelve to give a mean score ranging from one to four. The FAD has high Cronbach's alpha (.86), and split-half reliability (.83). Consistency between responses to the 12-item FAD, and related family variables provides validity evidence. 4) The Pediatric Symptom Checklist (PSC) measures parents' impressions of their child's psychosocial functioning and

takes 5 min. to complete. Parents complete 35 items reflecting a range of emotional and behavioral problems (e.g., “has trouble sleeping” or “feels sad, unhappy”) that are scored on a 3-point scale reflecting the rating that best fits their child (0 = never, 1=sometimes, 2 = often). Items are averaged to create a total scale. Higher scores reflect greater psychosocial problems/impairment. The psychometric properties of the PSC have been established across diverse populations of children and it has been validated in military populations. 5) The Parenting Scale (PS; ), a 30-item measure of parenting practices will also be completed. The PS has demonstrated adequate internal consistency and reliability, and correlates well with observational measures of dysfunctional discipline and child misbehavior. Demographics will be collected (5 min.). 6) The Personality Assessment Screener (PAS ) is a brief, 5 minute 22-item screener that is adapted from the larger response item Personality Assessment Inventory (PAI). It will be used to screen for the presence of co-morbid disorders. Items are scored with higher scores ranging from mild to marked risk (possible range 15-23). The Personality Assessment Observer (PAS-O) is designed as a parallel assessment to address the 22 corresponding items that the Veteran answered on the (PAS). It will be obtained through the spouse or partner of the Veteran and will help validate the Veterans’ (PAS) results.

Feasibility of collateral partner assessment: Where possible, a co-parent will be asked to complete the PSI, the PSC, PAS-O and demographics in order to examine whether it will be feasible to gather external evaluation of parent-child functioning at intake and post-treatment. This will be conducted via phone or web-based assessment.

Aim 2 Analysis Plan. The combination of the data collected will allow us to evaluate whether there is sufficient evidence to scale up to an RCT. Feasibility, acceptability and satisfaction: Descriptive statistics, including means, standard deviation, numbers, and percentages will be used to summarize feasibility and acceptability variables as the measures are continuous and there is no validated cut-off. Participant attendance at sessions exceeding 70% will indicate feasibility about timing and location of the group. Numbers of Veterans screened, assessed and enrolled vs. the number contacted will be examined to calculate a screening to enrollment ratio that will guide the timeline and costs for the future RCT and help evaluate overall feasibility and efficacy of recruitment strategies. At each stage, we will also assess reasons for opting out or dropping out to evaluate the barriers to participating and the feasibility of the proposed methods. A recruitment milestone of 8 Veterans (one cohort) enrolled within a 3-month period is necessary to meet the study goals and a good estimate of the feasibility and viability of scaling up recruitment for the planned RCT. Veteran satisfaction and feedback on the pre-treatment MIA as well as rating of interview fidelity on the MIA will be used to determine whether there is preliminary evidence that that the MIA is feasible and satisfactory. Veteran willingness to sign a release for partner contact, and number of successfully completed partner assessments will help determine the feasibility of collateral partner assessment of parent-child functioning in the RCT. Preliminary effectiveness: As formal significance testing is not the goal of this study, we will test for a signal that SAHP results in changes to the Veteran-reported primary outcomes at  $p < .10$ . Outcome analyses will be conducted following both Intention-to-treat and per protocol principles. That is, first, we will examine pre-to post-treatment changes in the

primary treatment outcomes for all individuals assessed (ITT). Second, we will examine pre-to post-treatment changes in the primary treatment outcomes from all Veterans completing the group. Outcomes will be analyzed using one-way within-subjects' ANOVA (i.e., repeated measures) to assess change from pre- to post-intervention at  $p < .10$ . Analyses will also evaluate differences between Veterans who do and do not complete Time 2 data. The goal of partner reported outcomes is to determine whether it will be feasible to gather these data. If successful, we will look for a signal that SAHP results in changes in the partner-reported outcomes, particularly changes in the support from parenting partner scale of the PSI.

| Schedule of Assessments                       |                   |          |        |                |                 |                          |
|---|-------------------|----------|--------|----------------|-----------------|--------------------------|
|   | Phone Screen      | Baseline | Weekly | Post-treatment | Measure Purpose |                          |
|   |                   | SAHP     | SAHP   | SAHP           |                 |                          |
| Reasons for opting out or dropping out | X                 | X        | X      | X              | Feasibility     |                          |
| Eligibility/Clinical Scales            | PCL-5             | X        | X      |                | X               | Eligibility/ Exploratory |
|   | PSI-SF            | X        |        |                |                 | Eligibility              |
|   | OSU TBI ID        |          | X      |                |                 | Eligibility              |
|   | MINI              |          | X      |                |                 | Eligibility              |
|   | BDI-II            |          | X      |                | X               | Eligibility/Exploratory  |
| AIM I (completed)                      | CEQ               |          |        | X              |                 | Treatment Credibility    |
|   | SAHP Specific     |          |        | X              |                 | Treatment Satisfaction   |
|   | Clinician notes   |          |        | X              |                 | Exploratory              |
| AIM II (ongoing)                       | SAHP Satisfaction |          |        |                | X               | Primary Outcome          |
|   | CEMI              |          | X      |                | x               | Feasibility Satisfaction |
|   | PSI- Partner      |          | X      |                | X               | Preliminary Outcomes     |
|   | PSC- Partner      |          | X      |                | X               | Preliminary Outcomes     |
|   | PAS-O             |          | X      |                | X               | Preliminary Outcomes     |
|   | CSQ               |          |        |                | X               | Primary Outcome          |

|   |            |   |   |   |   |                      |
|---|------------|---|---|---|---|----------------------|
| AIM I (completed) &
AIM II (ongoing) | PSI        | X | X | X | X | Preliminary Outcomes |
|   | APQ/APQ-PR | X | X | X | X | Preliminary Outcomes |
|   | FAD        | X | X | X | X | Preliminary Outcomes |
|   | PSC        | X | X | X | X | Preliminary Outcomes |
|   | PS         | X | X | X | X | Preliminary Outcomes |
|   | PAS        | X | X | X | X | Preliminary Outcomes |

\*Measure Names: **PSI-SF** (Parenting Stress Index), **OSU TBI ID** (Ohio State University Traumatic Brain Injury), **MINI** (Mini International Diagnostic Interview), **BDI II** (Beck Depression Inventory), **CEQ** (Credibility and Expectancy Questionnaire), **CSQ** (Client Satisfaction Questionnaire), **SAHP** Specific (Satisfaction questionnaire), **CEMI** (Client Evaluation and Interviewing Scale), **PSI** (Parenting Stress Index), **APQ** (Alabama Parenting Questionnaire), **FAD** (Family Assessment Device), **PSC** (Pediatric Symptom Checklist), **PS** (Parenting Scale), **PAS/PAS-O** (Personality Assessment Screener/Other)

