#### **B2. Veteran Inclusion Criteria:**

- 1) Age 18 years and older.

- 2) English speaking and able to provide written informed consent
- 3) Current parent to a child between the ages of 3 and 12. If the parent has more than one child within the target group, they will choose one of their children to be the index child for the purposes of SAHP (though we expect skills learned will translate to other children in the family). The child must reside with the Veteran or spend at least an average of two days per week with the Veteran.
- 4) Screen positive for elevated PTSD symptoms on the PTSD checklist for DSM 5 (PCL-5). The PCL-5 is a 20 item self-report measure of PTSD symptoms in the past month. Items are rated on a 5 point Likert scale (0 = not at all, 4= extremely) and participants endorse symptoms based on “a very stressful experience.” Items are summed with higher scores reflecting greater symptomatology. The measure evidences good reliability (Internal consistency = .96; test-retest = .84), discriminant and convergent validity and takes 5-10 min. to complete.
- 5) Screen positive (above the 85th percentile) for parent-child functioning problems based on Parenting Stress Index- Short Form; PSI-SF. All three subscales and the total stress scale on the short-form are highly correlated with those on the long-form (.97-.99), and is expected to take respondents about 10 minutes to complete. The total stress scale can successfully differentiate between different levels of risk for parent-child functioning problems and has strong convergent validity. High Cronbach's alpha scores have been reported across all scales, ranging from .88 to .95.

**B3. Exclusion Criteria:** The intent of exclusion criteria for this study is to ensure study participants can provide informed consent and understand assessments/group materials, detect and provide referrals for urgent treatment of suicidality, substance dependence or psychosis, and protect the group environment so that individuals who might be disruptive to the group process due to unmanaged symptoms of psychosis or inability to attend the group free from intoxicants are not enrolled. Therefore, at the intake assessment we will screen for the following conditions:

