**D11. Records retention information:** "The required records, including the investigator's research records, must be retained until disposition instructions are approved by the National Archives and Records Administration and are published in VHA's Records Control Schedule (RCS 10-1)." All de-identified data will be managed in accordance with the VHA Handbook 1605.1 APPENDIX B.

All original data will be stored at VA.

**D12. Reporting:** Any incidents involving theft or loss of data or storage media, unauthorized access of sensitive data or storage devices or non-compliance with security controls will be immediately reported to the IRB chair, Privacy Officer and Information Security Officer.

**D13. Data Analysis Software:** Data will be analyzed using the software programs R, SPSS and MPLUS that are already owned by the VA either using local copies of the software or through VA Informatics and Computing Infrastructure (VINCI).

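### The pre-post analysis labelled ITT is a two-time-point within-subjects ANOVA, so it omits every Veteran without a Time 2 score, and no missing-data method is given

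*Combined protocol and SAP*

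**What the plan says.** The Aim 2 Analysis Plan (section B9, Preliminary effectiveness) states: "Outcome analyses will be conducted following both Intention-to-treat and per protocol principles". It then describes two analyses. The first concerns change in the "primary treatment outcomes for all individuals assessed (ITT"). The second is restricted to Veterans who completed the group. One method serves both: "Outcomes will be analyzed using one-way within-subjects' ANOVA (i.e., repeated measures) to assess change from pre- to post-intervention", judged at p < .10.

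Three other statements bear on missing scores:

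- Under Measures and Data sources (B9), the outcomes are collected at intake and after session 8. For those who leave treatment, "In the case of drop-out, the post-treatment assessment will be scheduled within one week of what would have been session 8", in person or by phone.
- The Analysis Plan adds: "Analyses will also evaluate differences between Veterans who do and do not complete Time 2 data".
- D13 lists the software: "Data will be analyzed using the software programs R, SPSS and MPLUS". It ties none of these programs to a missing-data procedure.

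The documents mention no imputation, likelihood-based model, missing-data assumption or sensitivity analysis.

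**The concern.** An intention-to-treat label leads a reader to expect an estimate for everyone who entered the treatment phase. A two-time-point within-subjects ANOVA cannot give that unless every Veteran returns or the missing scores are filled in by some method, and none is named. The plan itself expects that some will not return, since it will compare those with and without Time 2 data. That comparison is a diagnostic and adds nobody to the estimate.

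If return depends on severity or on response to treatment, the estimated change is biased, and the direction cannot be known in advance. There is no control arm to offset the bias. The result is one part of the combined evidence for deciding whether to scale up to an RCT.

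The wording of the set is a lesser point. The feasibility list runs "Number and rates of Veterans contacted, screened, assessed, enrolled, retained", so assessment precedes enrolment, and B3 says "at the intake assessment we will screen for the following conditions". Read literally, the set could include Veterans excluded at intake. This does not affect a paired analysis, because they have no Time 2 score. It would matter for any method that uses all intake scores.

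**Working it through.** The plan states no drop-out rate, SD or expected change, so there is no figure of its own to reproduce.

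**1. What the named method uses.** With two time points, the within-subjects F equals the squared paired t. On a simulated set of 60 subjects with some Time 2 scores removed, F = 5.274 = t². A standard repeated-measures ANOVA routine rejected the incomplete data as unbalanced and ran only on the 49 subjects with both scores.

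**2. How many Veterans that leaves.** From the documents: minimum Aim 2 n = 48. Assumed: 30% leave treatment, and follow-up reaches a share s of them. Proportion without Time 2 data: m = 0.30 × (1 − s). Pairs: 48 × (1 − m). Completers: 48 × 0.70 = 33.6.

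| s | m | Pairs in the ITT analysis | Completers |
|---|---|---|---|
| 0 | 0.30 | 33.6 | 33.6 |
| 0.5 | 0.15 | 40.8 | 33.6 |
| 0.8 | 0.06 | 45.1 | 33.6 |

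The two analyses coincide only if follow-up reaches nobody.

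**3. Missing Veterans did not change.** If those observed change by c, the all-enrolled change is c(1 − m), and the relative overstatement is m/(1 − m). With c = −0.30 SD (assumed):

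| m | m/(1 − m) | All-enrolled change | Complete-case change |
|---|---|---|---|
| 0.06 | 6% | −0.28 | −0.30 |
| 0.15 | 18% | −0.26 | −0.30 |
| 0.20 | 25% | −0.24 | −0.30 |
| 0.30 | 43% | −0.21 | −0.30 |
| 0.40 | 67% | −0.18 | −0.30 |

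**4. Return depends on intake score.** Assumed: intake standard normal, true change −0.30 SD, pre-post correlation r = 0.5 or 0.7, and log-odds of return shifting by 0.5 or 1.0 per SD of intake. Let μ be the size of the shift in mean intake score among those who return. The expected complete-case change is −0.30 − (1 − r)μ if milder parents leave and −0.30 + (1 − r)μ if more severe parents leave. Numerical integration gives μ.

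| m | Log-odds per SD | μ | Milder leave (r = 0.7, 0.5) | More severe leave (r = 0.7, 0.5) |
|---|---|---|---|---|
| 0.15 | 0.5 | 0.073 | −0.32, −0.34 | −0.28, −0.26 |
| 0.15 | 1.0 | 0.133 | −0.34, −0.37 | −0.26, −0.23 |
| 0.33 | 0.5 | 0.157 | −0.35, −0.38 | −0.25, −0.22 |
| 0.33 | 1.0 | 0.277 | −0.38, −0.44 | −0.22, −0.16 |

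A simulation at n = 48 with 4,000 replicates per setting agrees with the 33% rows.

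**5. What the remedies recover.** In the step 4 simulation at 33% missing, a maximum-likelihood model on all available scores gave −0.29 to −0.31. In a simulation of the step 3 case it stayed at about −0.30 and so did not correct the bias. Setting change to zero for the missing Veterans recovered the all-enrolled values in the step 3 table. The two analyses address different kinds of loss.

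**6. Bias against sampling error.** The standard error of the paired change is about √(2(1 − r)/pairs). At 15% missing (40.8 pairs) it is √(1.0/40.8) = 0.157 for r = 0.5 and √(0.6/40.8) = 0.121 for r = 0.7. The step 4 bias of 0.02 to 0.07 SD is therefore about 0.2 to 0.4 standard errors. At 33% missing it is about 0.3 to 0.8.

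**The case against.** The strongest reply is that little hangs on this number. Aim 2 is a feasibility study. The plan says formal significance testing is not its goal. The schedule of assessments calls the parenting and family measures preliminary outcomes, and the explicit thresholds are attendance above 70% and 8 Veterans enrolled within 3 months. At modest missingness the bias is also small beside the sampling error (step 6), and the larger percentages need 30% or 40% of Time 2 scores to be missing. All of this stands, and it limits how serious the point is. It does not make the label accurate. If estimation rather than testing is the aim, bias in the estimate matters more.

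A second reply is that the plan already protects the analysis, by assessing drop-outs and comparing those with and without Time 2 data. Assessing drop-outs is a real safeguard and can make the ITT set larger than the completer set. But scheduling an assessment does not ensure that it takes place, and the comparison changes no estimate.

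A third is that the plan never says complete-case, and an ANOVA can be run on imputed data. That is fair: the restriction follows from the method named together with silence on missing data. As written, the analysis would default to pairs.

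Finally, the schedule table as it reads in the available text also marks these measures under the weekly column, against the intake and session 8 timing in Measures and Data sources. This may be a fault in how the table was extracted. Either way, the planned analysis is pre to post only.

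**Conclusion.** The concern holds. The named method does not deliver the stated intention-to-treat principle: it is complete-case for Time 2, though not limited to treatment completers. Its size depends on rates that the documents do not give. Across 6% to 40% missing, the change is overstated by 6% to 67% if the missing Veterans did not change. If return depends on intake severity, the bias is 0.02 to 0.07 SD at 15% missing and 0.05 to 0.14 SD at 33%, in either direction, under the assumed -0.30 SD change, correlations and log-odds. The plan should be corrected because a label promises more than the method gives and the remedy is cheap. No stated go/no-go threshold would be overturned by it.

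**What to change.** In the Aim 2 Analysis Plan:

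1. Define the ITT set as all Veterans enrolled after the intake eligibility assessment, whatever their attendance.
2. Estimate pre-post change with a maximum-likelihood linear mixed model (time effect, unstructured 2×2 covariance) on all available intake and post-treatment scores, including those from drop-out assessments. State that this covers missingness related to intake scores.
3. Add a sensitivity analysis that sets change to zero for Veterans without Time 2 data, reported as an estimate and not as a p < .10 test. This covers loss related to response.
4. Report how many Veterans dropped out and how many of them gave Time 2 data.
5. Keep the within-subjects ANOVA if wanted, labelled complete-case.

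The cost is revised wording and a few lines of code in R or Mplus, both already listed in D13. No new data are needed. The reported change may move in either direction.
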